10.1.12. Insurance Policy

In accordance with the provisions of the law and ICH GCP, the sponsor has an insurance policy intended to guarantee against possible damage resulting from the research.

The studies and/or experiments performed on behalf of the sponsor are specifically and expressly guaranteed.

It is advisable to underline that non-compliance with the research legal conditions is a cause for guarantee exclusion.

Unintentional infringements and vicarious liability are covered by the sponsor's insurance.

10.2. Appendix 2: Contraceptive Guidance

Contraceptive use by men or women should be consistent with local regulations regarding the methods of contraception for those participating in clinical studies. The following guidance is adapted from the guidelines of the Clinical Trials Facilitation Group [CTFG 2014].

10.2.1. Definition of a Woman of Childbearing Potential and Fertile Men

A woman is considered fertile following menarche and until becoming postmenopausal unless permanently sterile (see below).

If fertility is unclear (e.g. amenorrhea in adolescents or athletes) and a menstrual cycle cannot be confirmed before first dose of study treatment, additional evaluation should be considered.

Women in the following categories are not considered WOCBP:

1. Premenarchal.
2. Premenopausal female with one of the following:
 - Documented hysterectomy.
 - Documented bilateral salpingectomy.
 - Documented bilateral oophorectomy.

For participants with permanent infertility due to an alternate medical cause other than the above, (e.g. mullerian agenesis, androgen insensitivity), investigator discretion should be applied to determining study entry.

Note: Documentation can come from the study site personnel's: review of the participant's medical records, medical examination or medical history interview.

3. Postmenopausal female:
 - A postmenopausal state is defined as no menses for 12 months without an alternative medical cause.
 - High FSH levels in the postmenopausal range may be used to confirm a postmenopausal state in women not using hormonal contraception or hormonal replacement therapy (HRT). However, in the absence of 12 months of amenorrhea, confirmation with more than one measurement is required.
 - Females on HRT and whose menopausal status is in doubt will be required to use one of the non-estrogen hormonal highly effective contraception methods if they wish to continue their HRT during the study. Otherwise, they must discontinue HRT to allow confirmation of postmenopausal status before study enrollment.

For the purpose of this guidance, a man is considered fertile after puberty unless permanently sterile by bilateral orchidectomy.

10.2.2. Contraceptive Guidance

For the purpose of this guidance, methods that can achieve a failure rate of less than 1% per year when used consistently and correctly are considered as highly effective birth control methods. Such methods include:

- Combined (estrogen and progestogen containing) hormonal contraception associated with inhibition of ovulation:
 - Oral.
 - Intravaginal.
 - Transdermal.
- Progestogen-only hormonal contraception associated with inhibition of ovulation:
 - Oral.
 - Injectable.
 - Implantable.
- Intrauterine device.
- Intrauterine hormone-releasing system.
- Bilateral tubal occlusion.
- Vasectomized partner.
- Sexual abstinence.

Acceptable birth control methods that result in a failure rate of more than 1% per year include:

- Progestogen-only oral hormonal contraception, where inhibition of ovulation is not the primary mode of action.
- Male or female condom with or without spermicide.
- Cap, diaphragm or sponge with spermicide.

NOTE: Due to the potential of encorafenib to induce CYP3A4, hormonal agents (including but not limited to birth control patch, vaginal ring, oral, injectable or implanted contraceptives) are permissible only when combined with other highly effective or acceptable methods of contraception.

10.3. Appendix 3: Non-exhaustive List of Concomitant Medications

These lists are not all inclusive. Please refer to the following websites provided for further guidance:

- <https://www.fda.gov/drugs/drug-interactions-labeling/drug-development-and-drug-interactions-table-substrates-inhibitors-and-inducers>
- <https://drug-interactions.medicine.iu.edu/MainTable.aspx>

Table 11: List of Cytochrome P450 Substrates to be used with Caution (CYP2C8, CYP2C9, CYP2C19 and CYP3A)

CYP2C8	CYP2C9	CYP2C19	CYP3A	
Amodiaquine	Acenocoumarol	Clopidogrel	Alfentanil[a],[b]	Ergotamine[b]
Cerivastatin	Celecoxib	Diazepam	Alpha-dihydroergocryptine[a]	Everolimus[a]
Repaglinide	Diclofenac	Esoprazole	Alprazolam	Felodipine[a]
Rosiglitazone	Glipizide	Lansoprazole	Amlodipine	Fentanyl[b]
Torasemide	Irbesartan	Moclobemide	Aplaviroc	Fluticasone[a]
	Losartan	Omeprazole	Aprepitant[a]	Indinavir[a]
	Phenytoin[b]	Pantoprazole	Aripiprazole	Lopinavir[a]
	Piroxicam	Phenobarbitone	Atorvastatin	Lovastatin[a]
	S-isuprofen	Phenytoin[b]	Boceprevir	Maraviroc[a]
	Sulfamethoxazole	Proguanil	Brecanavir	Midazolam[a]
	Tolbutamide	Rabeprazole	Brotizolam[a]	Nifedipine
	Torasemide	S-mephenytoin	Budesonide[a]	Nisoldipine
			Buspirone[a]	Nitrendipine
			capravirine	Perospirone[a]
			casopitant	Quinine
			Conivaptan[a]	Saquinavir[a]
			Cyclosporine[b]	Sildenafil[a]
			Darifenacin[a]	Simvastatin[a]
			Darunavir[a]	Sirolimus[a],[b]
			Diazepam	Telaprevir
			Diergotamine[b]	Tipranavir[a]
			Diltiazem	Tolvaptan
			Ebastine[a]	Triazolam[a]
			Eletriptan[a]	Verapamil
			Eplerenone[a]	

Abbreviations: CYP = cytochrome P450; FDA = Food and Drug Administration; US = United States.

*Table was compiled from the Indiana University School of Medicine's "Clinically Relevant" table, a list by the US FDA (<http://fda.gov/Drugs/DevelopmentApprovalProcess/DevelopmentResources/DrugInteractionsLabeling/ucm080499.htm>) and the University of Washington's Drug Interaction Database. The list is not necessarily exhaustive of every possible substrate.

[a] Sensitive substrates: Drugs whose plasma area under concentration-time curve values have been shown to increase 5-fold or higher when co-administered with a potent inhibitor of the respective enzyme.

[b] Substrates with narrow therapeutic index: Drugs whose exposure-response indicates that increases in their exposure levels by the concomitant use of potent inhibitors may lead to serious safety concerns (e.g. Torsade de Pointes).

Table 12: List of Cytochrome P450 substrates to be used with Caution (CYP2B6)

CYP2B6*
bupropion[a]
Cyclophosphamide
Efavirenz[a]
Ifosfamide
Methadone
Thiotepa
Abbreviations: CYP = cytochrome P450; FDA = Food and Drug Administration; US = United States.
*Table was compiled from the Indiana University School of Medicine's "Clinically Relevant" table, a list by the US FDA (http://fda.gov/Drugs/DevelopmentApprovalProcess/DevelopmentResources/DrugInteractionsLabeling/ucm080499.htm) and the University of Washington's Drug Interaction Database. The list is not necessarily exhaustive of every possible substrate.
[a] Sensitive substrates: The area under the concentration-time curves of these substrates were not increased by 5-fold or more with a CYP2B6 inhibitor, but they represent the most sensitive substrates studied with available inhibitors evaluated to date.

Table 13: List of Inhibitors of Uridine Diphosphate-glucuronosyl Transferase 1A1 to be used with Caution

Inhibitors of UGT1A1	Atazanavir, erlotinib, flunitrazepam, gemfibrozil, indinavir, ketoconazole, nilotinib, pazopanib, propofol, regorafenib, sorafenib
Abbreviations: UGT1A1 = Uridine diphosphate-glucuronosyl transferase.	

Table 14: Moderate Cytochrome P450 3A4 inhibitors to be Administered with Caution when co-administered with Encorafenib

Ciprofloxacin	Erythromycin
Fluconazole	Amprenavir
Verapamil	Imatinib
Atazanavir	Schisandra sphenanthera
Aprepitant	Casopitant
Cyclosporine	Cimetidine
Tofisopam	Dronedarone
Fosamprenavir	Darunavir
Diltiazem	
Reproduced from http://fda.gov/Drugs/DevelopmentApprovalProcess/DevelopmentResources/DrugInteractionsLabeling/ucm080499.htm	

Table 15: Breast Cancer Resistance Protein and P-glycoprotein inhibitors/inducers to be used with caution

Transporter	Gene	Inhibitor [a]	Induce [b]
BCRP	ABCG2	Cyclosporine, elacridar (GF120918), eltrombopag, gefitinib	Not known
P-gp	ABCB1	Amiodarone, azithromycin, captopril, carvedilol, clarithromycin, conivaptan, cyclosporine, diltiazem, dronedarone, erythromycin, felodipine, itraconazole, ketoconazole, lopinavir and ritonavir, quercetin, quinidine, ranolazine, verapamil	Avasimibe, carbamazepine, phenytoin, rifampin, St John's wort, tipranavir/ritonavir

Abbreviations: BCRP = breast cancer resistance protein; P-gp = P-glycoprotein.
 Reproduced from
<http://fda.gov/Drugs/DevelopmentApprovalProcess/DevelopmentResources/DrugInteractionsLabeling/ucm080499.htm>

[a] Inhibitors listed for P-gp are those that showed >25% increase in digoxin area under the concentration-time curve or otherwise indicated if substrate is other than digoxin.

[b] Inducers listed for P-gp are those that showed >20% decrease in digoxin area under the concentration-time curve or otherwise indicated if substrate is other than digoxin.

Table 16: Substrates of Breast Cancer Resistance Protein, Organic Anionic Transporters, Organic Anion Transporting Polypeptides, Organic Cationic Transporters and P-glycoprotein, to be administered with caution

BCRP	Imatinib, irinotecan, lapatinib, methotrexate, mitoxantrone, rosuvastatin, sulfasalazine, topotecan
P-gp	Aliskiren, ambrisentan, colchicine, dabigatran etexilate, digoxin, everolimus, fexofenadine, imatinib, lapatinib, maraviroc, nilotinib, posaconazole, ranolazine, saxagliptin, sirolimus, sitagliptin, talinolol, tolvaptan, topotecan
OCT2	Amantadine, amiloride, cimetidine, dopamine, famotidine, memantine, metformin, pindolol, procainamide, ranitidine, varenicline, oxaliplatin
OAT1	Adefovir, captopril, furosemide, lamivudine, methotrexate, oseltamivir, tenofovir, zalcitabine, zidovudine
OAT3	Acyclovir, bumetanide, ciprofloxacin, famotidine, furosemide, methotrexate, zidovudine, oseltamivir acid, (the active metabolite of oseltamivir), penicillin G, pravastatin, rosuvastatin, sitagliptin
OATP1B1	Atrasentan, atorvastatin, bosentan, ezetimibe, fluvastatin, glyburide, SN-38 (active metabolite of irinotecan), rosuvastatin, simvastatin acid, pitavastatin, pravastatin, repaglinide, rifampin, valsartan, olmesartan
OATP1B3	Atorvastatin, rosuvastatin, pitavastatin, telmisartan, valsartan, olmesartan

Abbreviations: BCRP= breast cancer resistance protein; OAT = organic anion transporter, organic anion transporting polypeptide; organic cationic transporter; P-gp = P-glycoprotein.
 Reproduced from
<http://fda.gov/Drugs/DevelopmentApprovalProcess/DevelopmentResources/DrugInteractionsLabeling/ucm080499.htm>

Table 17: List of Potential QT Prolonging Drugs

Drug	QT Risk	Comment
Alfuzosin	Possible risk	
Amantadine	Possible risk	
Amiodarone	Known risk	Females>Males, TdP risk regarded as low
Amitriptyline	Conditional risk	Risk of TdP with overdosage. Substrate of CYP2C19
Arsenic trioxide	Known risk	
Astemizole	Known risk	Not available in China. Substrate for CYP3A4
Atazanavir	Possible risk	
Azithromycin	Possible risk	Rare reports
Bepridil	Known risk	Females>Males
Chloral hydrate	Possible risk	
Chloroquine	Known risk	
Chlorpromazine	Known risk	
Ciprofloxacin	Conditional risk	Drug metabolism inhibitor; risk for drug interactions
Cisapride	Known risk	Substrate for CYP3A4
Citalopram	Known risk	
Clarithromycin	Known risk	Substrate for CYP3A4
Clomipramine	Conditional risk	
Clozapine	Possible risk	
Desipramine	Conditional risk	Risk of TdP with overdosage
Diphenhydramine	Conditional risk	Risk of QT increase/TdP in overdosages
Disopyramide	Known risk	Females>Males
Dofetilide	Known risk	
Dolasetron	Possible risk	
Domperidone	Known risk	
Doxepin	Conditional risk	
Dronedarone	Possible risk	Substrate for CYP3A4
Droperidol	Known risk	
Eribulin	Possible risk	
Erythromycin	Known risk	Females>Males. Substrate for CYP3A4
Escitalopram	Possible risk	
Famotidine	Possible risk	
Felbamate	Possible risk	
Fingolimod	Possible risk	
Flecainide	Known risk	

Drug	QT Risk	Comment
Fluconazole	Conditional risk	Drug metabolism inhibitor; risk for drug interactions
Fluoxetine	Conditional risk	
Foscarnet	Possible risk	
Fosphenytoin	Possible risk	
Galantamine	Conditional risk	
Gatifloxacin	Possible risk	
Gemifloxacin	Possible risk	
Granisetron	Possible risk	
Halofantrine	Known risk	Females>Males
Haloperidol	Known risk	When given intravenously or at higher than recommended doses, risk of sudden death, QT prolongation and torsades increases. Substrate for CYP3A4
Ibutilide	Known risk	Females>Males
Imipramine	Conditional risk	Risk of TDP in overdosage
Indapamide	Possible risk	
Isradipine	Possible risk	
Itraconazole	Conditional risk	Drug metabolism inhibitor-risk for drug interactions
Ketoconazole	Conditional risk	Drug metabolism inhibitor
Levofloxacin	Possible risk	
Levomethadyl	Known risk	Not available in the US.
Lithium	Possible risk	
Mesoridazine	Known risk	
Methadone	Known risk	Females>Males. Substrate for CYP3A4
Moexipril/HCTZ	Possible risk	
Moxifloxacin	Known risk	
Nicardipine	Possible risk	
Nortriptyline	Conditional risk	
Octreotide	Possible risk	
Ofloxacin	Possible risk	
Ondansetron	Possible risk	
Oxytocin	Possible risk	
Paliperidone	Possible risk	
Paroxetine	Conditional risk	
Pentamidine	Known risk	Females>Males
Perflutren lipid microspheres	Possible risk	
Pimozide	Known risk	Females>Males. Substrate for CYP3A4

Drug	QT Risk	Comment
Probucol	Known risk	
Procainamide	Known risk	
Protriptyline	Conditional risk	
Quetiapine	Possible risk	Substrate for CYP3A4
Quinidine	Known risk	Females>Males. Substrate for CYP3A4
Ranolazine	Possible risk	
Risperidone	Possible risk	
Ritonavir	Conditional risk	Substrate for CYP3A4
Roxithromycin	Possible risk	
Sertindole	Possible risk	
Sertraline	Conditional risk	
Solifenacin	Conditional risk	
Sotalol	Known risk	Females>Males
Sparfloxacin	Known risk	
Tacrolimus	Possible risk	Substrate for CYP3A4
Telithromycin	Possible risk	Substrate for CYP3A4
Terfenadine	Known risk	Substrate for CYP3A4
Thioridazine	Known risk	
Tizanidine	Possible risk	
Trazodone	Conditional risk	Substrate for CYP3A4
Trimethoprim-Sulfa	Conditional risk	
Trimipramine	Conditional risk	
Vandetanib	Known risk	
Vardenafil	Possible risk	Substrate for CYP3A4
Venlafaxine	Possible risk	
Voriconazole	Possible risk	
Ziprasidone	Possible risk	

Abbreviations: CYP = cytochrome P450; TDP = Torsades de Pointes; US = United States.
 Additional agents can be found at <https://www.crediblemeds.org>
 Classification according to the Qtdrugs.org Advisory Board of the Arizona CERT.

Table 18: Strong Cytochrome P450 3A4 Inhibitors and Strong/moderate Cytochrome P450 Inducers to be Prohibited when Co-administered with Encorafenib

Strong Inhibitors	
boceprevir	nefazodone
Clarithromycin	Nelfinavir
Conivaptan	Posaconazole
Indinavir	Ritonavir
Itraconazole	Saquinavir
Ketoconazole	Telithromycin
Lopinavir	Troleandomycin
Telaprevir	Grapefruit juice (citrus paradisi fruit juice)
Mibefradil	Voriconazole
Strong Inducers	
Avasimibe	Rifampin
Carbamazepine	St. John's wort
Phenytoin	
Moderate Inducers	
Bosentan	Efavirenz
Etravirine	Modafinil
Reproduced from https://fda.gov/Drugs/DevelopmentApprovalProcess/DevelopmentResources/DrugInteractionsLabeling/ucm080499.htm	

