Non-cutaneous malignancies with RAS mutation	As for other BRAF inhibitors and based on its mechanism of action, encorafenib may promote malignancies associated with RAS mutation associated with activation of RAS	Routine cancer detection and treatment as well as preventive measures for different known risk

Important Risks	Summary of Data/Rationale for Risk	Mitigation measures
	
through mutation or other mechanisms. No cases of non-cutaneous malignancy with RAS mutation possibly related to encorafenib were identified from the pooled safety data of the clinical development program, however due to the seriousness of this class-effect risk, non-cutaneous carcinoma is considered an important potential risk.
	
factors of different cancers will be performed.
 
Dose modifications are outlined in Appendix 10.4.

Over-exposure due to concomitant use with strong and moderate CYP450 3A4 inhibitors	
Encorafenib is primarily metabolised by CYP3A4. Based on the PK data, the use of strong CYP3A4 inhibitors was not allowed during clinical studies. Concomitant administration of encorafenib and strong or moderate CYP3A4 inhibitors may lead to increased encorafenib exposure and potential increase in toxicity.
	
Drug-drug interactions properties of encorafenib are described in the Investigator's Brochure for encorafenib.
 
The use of strong inhibitors of CYP3A4 is prohibited.
 
Concomitant use of moderate CYP3A4 inhibitors should be avoided. If use of moderate CYP3A4 inhibitors is unavoidable and no alternatives are available, short-term use (≤ 30 days) following discussion with the sponsor may be permitted with accompanying dose reduction to one-half of the encorafenib dose before use of moderate CYP3A4 inhibitors (or as close as can be achieved without exceeding the target dose).

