6.5.1.1. Authorized Therapies requiring Caution and/or Action

Participants should be closely monitored for the occurrence of adverse events whilst taking these therapies.

6.5.1.1.1. *Cytochrome P450 and Uridine 5'-diphospho-glucuronosyltransferase Substrates and Inhibitors*

Encorafenib is a reversible inhibitor of CYP2B6, CYP2C9, CYP3A4 and uridine 5'-diphospho-glucuronosyltransferase (UGT)1A1. It is also a time-dependent inhibitor of CYP3A4. Permitted medications to be used with caution in this study include those that are sensitive substrates of CYP2B6, CYP2C8, CYP2C9, CYP2C19, CYP3A4 (see Table 11 and Table 12) and UGT1A1 (see Table 13) or those substrates that have a narrow therapeutic index.

There is a potential for encorafenib to induce CYP3A4, which may reduce the effectiveness of hormonal contraception methods. At least one form of non-hormonal contraception is therefore required during participation in this study (see Section 5.3.1). Caution should also be exercised in participants receiving concomitant treatment with other drugs that are substrates of CYP3A4 as the efficacy of these drugs could be reduced when administered with encorafenib.

Encorafenib has been identified in vitro to be metabolized by CYP3A4 and to a lesser extent by CYP2C19. The use of strong inhibitors of CYP3A4 is prohibited (see Section 6.5.2). Concomitant use of moderate CYP3A4 inhibitors (see Table 14) while on study should be avoided. If use of moderate CYP3A4 inhibitors is unavoidable and no alternatives are available, short-term use (≤ 30 days) following discussion with the sponsor may be permitted with accompanying dose reduction to one-half of the encorafenib dose before use of moderate CYP3A4 inhibitors (or as close as can be achieved without exceeding the target dose). The encorafenib dose that was taken before initiating the CYP3A4 inhibitor may be resumed after the inhibitor has been discontinued for three to five elimination half-lives. Strong inhibitors of CYP2C19 should be used with caution when coadministered with encorafenib.

6.5.1.1.2. *Transporter Substrate and Inhibitors*

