In vitro data showed that encorafenib is a substrate of the transporter P-glycoprotein (P-gp) and a breast cancer resistance protein (BCRP) inhibitor. Use of medications that are known to inhibit or induce P-gp or BCRP should be used with caution (see Table 15). Encorafenib is also a potent inhibitor of the renal transporters, organic anionic transporter (OAT)1, OAT3 and organic cationic transporter (OCT)2 and the hepatic transporter organic anion-transporting peptide (OATP1)B1 and OATP1B3. The co-administration of drugs that are known to be sensitive or narrow therapeutic index substrates of BCRP, P-gp, OAT1, OAT3, OCT2, OATP1B1 and OATP1B3 should be used with caution (see Table 16).

6.5.1.1.3. *Drugs with a Conditional or Possible Risk to Prolong the QT Interval and/or Induce Torsade de Pointes*

Investigators should use caution when administering encorafenib with concomitant medications with a known, conditional or possible risk to prolong the QT interval and/or induce Torsade de Pointes (see Table 17). Participants receiving such medications must be carefully monitored for potentiation of toxicity due to any individual concomitant medication and may require dose titration of the concomitant medication.

6.5.2. **Prohibited Medications and Therapeutic/Diagnostic Procedures**

The following therapies are prohibited during screening and the Treatment Period (unless otherwise noted). There are no prohibited therapies during the post-treatment Follow-up Period. None of the concomitant therapies and therapeutic/diagnostic procedures listed below are allowed during the treatment phase:

- Anticancer agents such as cytotoxic chemotherapy small-molecule targeted agents, biological agents, immune response modifiers or hormonal therapy.
- Local therapies which could interfere with treatment (e.g. surgical excision or ablation of lesions are not permitted without sponsor approval).
- Investigational drugs (other than study treatments) and devices.
- Radiation therapy (not including palliative radiotherapy at focal sites that covers $\leq 10\%$ of the bone marrow reserve). Calculation of the percentage of active bone marrow reserve can be performed using information in **Table 6 [Hindorf, 2010]**.

Note: The participant must have clear measurable disease outside the radiated field.

Note: Radiation therapy to a symptomatic solitary lesion or to the brain may be considered on a case-by-case basis after consultation with the sponsor's medical monitor.

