Note: Administration of palliative radiation therapy will be considered clinical progression.

- Herbal preparations/medications. Participants should stop using herbal medications (including use of St. John's Wort [*hypericum perforatum*] and traditional Chinese medicine

susceptible to be a moderate or strong inhibitor or inducer of CYP3A4/5) 7 days before the first dose of study treatment.

- Concomitant systemic strong CYP3A4 inhibitors or moderate/strong inducers which are likely to significantly increase or decrease respectively encorafenib exposure (listed in Table 18).

Table 6: The percentage of total red marrow present at different skeletal sites in a healthy adult

Skeletal site	Percentage of red marrow
Cranium	7.6
Mandible	0.8
Scapulae	2.8
Clavicles	0.8
Sternum	3.1
Ribs	16.1
Cervical vertebrae	3.9
Thoracic vertebrae	16.1
Lumbar vertebrae	12.3
Sacrum	9.9
Os coxae	17.5
Femora, upper half	6.7
Femora, lower half	0
Tibiae, fibulae, patellae	0
Ankle and foot bones	0
Humeri, upper half	2.3
Humeri, lower half	0
Ulnae, radii	0
Wrist and hand bones	0

If another therapy and/or therapeutic/diagnostic procedure has to be prescribed in the interests of the participant's health, the decision to discontinue the participant from the study should be taken by the investigator.

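### Protocol Section 6.5.1.1.2 and Table 15 list under caution 11 agents that Section 6.5.2 and Table 18 prohibit; four strong inducers are the most open to misreading

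*Protocol*

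**What the plan says.** **The caution text.** Protocol Section 6.5.1.1 covers authorized therapies that need caution or action. Its subsection 6.5.1.1.2 describes encorafenib as a P-gp substrate in vitro and continues: "Use of medications that are known to inhibit or induce P-gp or BCRP should be used with caution". It cites Table 15 in Appendix 3, titled "Breast Cancer Resistance Protein and P-glycoprotein inhibitors/inducers to be used with caution".

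**The prohibition.** Section 6.5.2 opens its list with "None of the concomitant therapies and therapeutic/diagnostic procedures listed below are allowed during the treatment phase". The list includes "Concomitant systemic strong CYP3A4 inhibitors or moderate/strong inducers which are likely to significantly increase or decrease respectively encorafenib exposure" and refers to Table 18, whose title ends "Strong/moderate Cytochrome P450 Inducers to be Prohibited when Co-administered with Encorafenib".

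**Text that bears on which one governs.**
- Section 6.5.1 allows necessary concomitant medication except where the protocol says otherwise.
- Section 6.5.1.1.1, immediately before 6.5.1.1.2, restates the ban on strong CYP3A4 inhibitors and points to Section 6.5.2.
- Exclusion criterion 7 bars prohibited medication in the week before treatment and concomitantly. Its notes name St John's wort, and note ii covers inducers.
- Section 6.5.2 also names St John's wort in its bar on herbal products.
- Section 6.5 tells investigators to contact the sponsor if they are unsure about a medication.

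**The concern.** The two tables overlap, and the overlap is not explained by their serving different purposes. Table 15 is cited because encorafenib is a P-gp substrate; Table 18 is cited because its agents are expected to change encorafenib exposure materially. Both tell the site what a co-drug may do to encorafenib. A site that looks up rifampin, carbamazepine or clarithromycin through the authorized-therapy section finds caution. A site that looks it up through the prohibited-therapy section finds a ban.

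What is at stake is participant safety and the reading of a very small study. A strong inhibitor could raise exposure and toxicity. A strong inducer could lower exposure and make a DLT less likely to appear. The exposure requirement for the Dose-Determining Set counts milligrams administered, so a participant on an inducer could take every capsule and remain evaluable while under-exposed. With 3 to 6 evaluable participants, one such case carries weight.

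**Working it through.** No sample size or error rate is involved, and the plan states no figure to reproduce. The check is a comparison of lists, with combination products split into single agents.

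**Inputs, all from Protocol Appendix 3**
- Table 15, P-gp inhibitors: 19 agents (18 entries, with lopinavir and ritonavir counted as two).
- Table 15, P-gp inducers: 6 entries, 7 agents (tipranavir/ritonavir counted as two).
- Distinct P-gp agents: 19 + 7 − 1 = 25, because ritonavir is in both columns. The BCRP row adds elacridar, eltrombopag and gefitinib, which gives 28 for the whole table.
- Table 18: 18 strong inhibitors + 5 strong inducers + 4 moderate inducers = 27.
- Table 14: 17 moderate CYP3A4 inhibitors.

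**Overlap of Table 15 with Table 18**

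| Table 18 group | Agents in group | Also in Table 15 | Which |
|---|---|---|---|
| Strong inhibitors | 18 | 6 | clarithromycin, conivaptan, itraconazole, ketoconazole, lopinavir, ritonavir |
| Strong inducers | 5 | 5 | avasimibe, carbamazepine, phenytoin, rifampin, St John's wort |
| Moderate inducers | 4 | 0 | none |
| Total | 27 | 11 | |

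That is 11/25 = 44% of the P-gp agents: 6 of 19 inhibitors, and 5 of 6 inducer entries that are themselves prohibited inducers. The sixth inducer entry, tipranavir/ritonavir, contains a prohibited inhibitor.

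**How many have no ban close by.** Section 6.5.1.1.1 restates the class ban for the 6 inhibitors, and St John's wort is named in exclusion 7 and Section 6.5.2. So 11 − 6 − 1 = 4: avasimibe, carbamazepine, phenytoin and rifampin. Their ban is not repeated within Section 6.5.1.1, and the only place it names them is Table 18. Section 6.5.1.1 mentions CYP3A4 induction only as something encorafenib may do.

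**Is precedence stated?** Neither Section 6.5.1.1.2 nor Table 15 with its footnotes refers to Table 18 or sets its agents apart. The other caution tables (11 to 14, 16 and 17) do not refer to it either.

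**A related gap.** Five Table 15 agents are also in Table 14: cyclosporine, diltiazem, dronedarone, erythromycin and verapamil. For these, Section 6.5.1.1.1 is stricter than caution: avoid them, or allow at most 30 days after discussion with the sponsor, at half the encorafenib dose.

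**Why one participant matters.** The dose is acceptable if the DLT rate is below 33%. The possible results near that limit are 0/3 = 0% (accepted), 1/3 = 33.3% (referred to the steering committee), 1/6 = 16.7% (accepted) and 2/6 = 33.3% (not accepted). One participant's classification can change the outcome.

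**The case against.** The strongest reply is that the protocol already answers the question. Section 6.5.2 is categorical, Section 6.5.1 yields to it, exclusion 7 covers concomitant use, and an investigator in doubt is told to ask the sponsor. Nothing says that a Table 18 agent may be used. This stands: a careful reader reaches the prohibition, so the fault is conflicting wording without a precedence rule. It is not an actual permission.

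A second reply is that Table 15 concerns transporters and Table 18 concerns CYP3A4, so the lists may differ. This carries less weight, because Section 6.5.1.1.2 invokes Table 15 for its effect on encorafenib as a substrate, which is the same question that Table 18 addresses. The reply does hold for nine other Table 18 agents that appear in Tables 11 to 13, 16 or 17 as substrates, UGT1A1 inhibitors or QT-prolonging drugs. A reader might count those as contradictions too, but they answer different questions.

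A third reply is that Section 6.5.2 bans only systemic use, so caution could refer to topical products. Table 15 has no such limit, and its footnotes define P-gp entries by changes in digoxin AUC.

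A reader might also take Table 2, which mentions a ban on strong inhibitors only, as further evidence that inducers were overlooked. It is not: that row concerns over-exposure, where inducers do not belong.

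**Conclusion.** The conflict is real and the count is exact: 11 agents are under caution in one place and prohibited in another. Its practical size is modest. The prohibition governs, the inhibitor ban is restated next to the conflicting text, and St John's wort is barred by name. The part most open to misreading is four strong inducers. The counts measure conflicting entries. They say nothing about how likely it is that such a drug would be prescribed, and the documents offer no basis for that. The effect on DLTs or PK is therefore a possibility without an estimate, and it assumes that a site relies on Table 15 alone.

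A reader might infer that the SAP needs a new flag or a PK exclusion for interacting drugs, since its PK and Dose-Determining Set rules name none. The documents do not support that step. SAP Section 6.8 already reviews, classifies and lists all deviations before database lock or any snapshot. Section 6.7.2.2 lists all concomitant medications, and the outlier rule can deal with an anomalous concentration. An exclusion window would have to be assumed, for example 7 days borrowed from the eligibility washout. With three participants, one exclusion would leave 3 − 1 = 2, below the SAP's minimum of 3 for full summary statistics.

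**What to change.** In Protocol Section 6.5.1.1 and at the head of Appendix 3:

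1. State that Table 18 overrides Tables 11 to 17.
2. Restate the ban on strong and moderate CYP3A4 inducers beside the existing ban on strong inhibitors.
3. Remove the 11 agents from Table 15, or mark each as prohibited with a reference to Table 18.
4. For cyclosporine, diltiazem, dronedarone, erythromycin and verapamil, point to the stricter rule in Section 6.5.1.1.1.

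The cost is a few lines of text and marks against table entries. Design, data collection and the SAP stay as they are.
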